13.3.3 Protocol Deviations

Any protocol deviations will be listed and reasons for exclusion from the analysis populations will be summarized

13.4 General Considerations

Unless stated otherwise, continuous variables will be summarized showing the number of non-missing values (n), mean, standard deviation, median, minimum and maximum and categorical variables will be summarized showing the number and percentage of patients falling in each category. Summaries will be presented for data recorded pre-treatment, during each 25 day dosing phase (placebo and GWP42003-P) and during the OLE phase separately.

13.5 Accountability and Background Characteristics

13.5.1 Enrollment and Disposition

All patients (screened, treated, completing the study and those prematurely terminated IMP) will be accounted for in the enrollment and disposition summary tables.

13.5.2 Baseline and Demographic Characteristics

Age, sex, race (as allowed per local regulations) and any other demographic or baseline characteristics will be summarized, using appropriate summary statistics.

13.5.3 Medical History

Previous and current medical conditions will be summarized by system organ class, including details of the duration of epilepsy and the types of seizures currently experienced by the patients.

13.5.4 Concomitant Medication

Concomitant medications taken prior to and during the study will be summarized, by medication class and active ingredients. Summaries of medications taken during the IMP treatment phases and during OLE will be presented separately.

13.6 Endpoints and Statistical Methods

13.6.1 Primary Endpoint(s)

The primary endpoints of the study are the PK parameters (C_{max} , t_{max} , $AUC_{(0-\infty)}$, $AUC_{(0-t)}$, $t_{1/2}$) of the following analytes:

- CLB
- N-CLB
- CBD
- CBD major metabolites

13.6.2 Secondary Endpoint(s)

The secondary endpoints of the study are the safety parameters (see [Section 13.6.4](#)) and the PK parameters (C_{max} , t_{max} , $AUC_{(0-\infty)}$, $AUC_{(0-t)}$, $t_{1/2}$) of the following analytes:

- THC
- THC major metabolites

13.6.3 Pharmacokinetics

Calculation of PK parameters will be based on actual blood sampling times [h] (relative to the corresponding administration time) rounded to two decimal digits with negative pre-dose times set to zero. Plasma concentrations of CLB, N-CLB, VPA, STP, LEV, TPM, CBD, CBD major metabolites, THC and THC major metabolites will be displayed graphically, summarized and listed. For descriptive statistics, values below the lower limit of quantification of the assay (LLOQ) will be excluded from any calculations. Descriptive statistics of concentrations will be calculated if at least half of the individual data points that have been measured are equal to or above the LLOQ.

For calculation of the PK parameters, the following rules will be applied:

At time zero and at time points in the lag-time between time zero and the first quantifiable concentration, concentrations below the LLOQ will be set to zero. All other concentrations below the LLOQ will not be used in calculations.

Variables derived from plasma concentrations:

- Concentration maximum (C_{\max}): Highest observed plasma concentration of the measured concentration-time profile. Dimension: [amount / volume].
- Terminal half-life $t_{1/2} = \ln(2)/\lambda_z$.
- The rate constant of the terminal phase λ_z will be determined by linear regression of log-transformed concentration data after the time of maximum concentration. A sequence of terminal elimination rate constants will be created by linear regression. Linear regressions are repeated using the last three points with a quantifiable concentration, the last four points, the last five points etc. For each regression, an adjusted R^2 is computed. The regression with the largest adjusted R^2 is selected to estimate the terminal half-life. Dimension: [time].
- Area under the concentration-time curve from administration until the last sampling point (t) equal or above the LLOQ $AUC_{(0-t)}$ will be calculated by the linear trapezoidal formula. Dimension: [time • amount / volume].
- Area under the concentration-time curve extrapolated to infinity: $AUC_{(0-\infty)} = AUC_{(0-t)} + C_{\text{last}}/\lambda_z$ and C_{last} is the concentration observed at the last time point with a quantifiable concentration, λ_z refers to the terminal elimination rate constant. Dimension: [time • amount / volume].
- Time of maximum concentrations: T_{\max} will be taken as the time after administration at which C_{\max} occurs. Dimension: [time].
- PK parameters for each analyte will be summarized for the two treatment phases of the study separately, as appropriate.
- In order to assess whether the presence of CBD alters the PK profile of CLB (or N-CLB), a standard 90% confidence interval (CI) approach for the between group ratios of geometric means of C_{\max} , $AUC_{(0-t)}$, and $AUC_{(0-\infty)}$ will

be carried on logarithm scale using a linear mixed effect model with treatment (CLB or CLB+CBD) as a fixed effect and subject as a random effect. The no-effect boundary will be set between 0.5 and 2.0 and if the 90% CI for the ratio of the geometric means of a PK variable falls within the interval [0.5, 2.0], a lack of meaningful effect will be declared.

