6.1 Inclusion Criteria

For inclusion in the study patients must fulfil ALL of the following criteria:

- 6.1.1 Male or female patients aged 18 to 65 years inclusive.
- 6.1.2 Patient must have epilepsy as determined by the investigator and be taking CLB.
- 6.1.3 Patient must have a documented magnetic resonance imaging/computerized tomography of the brain that ruled out a progressive neurologic condition.
- 6.1.4 Patient must have experienced at least one seizure of any type (i.e., convulsive: tonic-clonic, tonic, clonic, atonic; focal: focal seizures with retained consciousness and a motor component, focal seizures with impaired consciousness focal seizures evolving to bilateral secondary generalization) within the two months prior to randomization.
- 6.1.5 Patients must be taking CLB and no more than two other AEDs during the course of the study.
- 6.1.6 AED(s), including CLB, must be stable for four weeks prior to screening and regimen must remain stable throughout the duration of the blinded phase of the study.

- 6.1.7 Intervention with vagus nerve stimulation (VNS) and/or ketogenic diet must be stable for four weeks prior to baseline and patient/caregiver must be willing to maintain a stable regimen throughout the blinded phase of the study.
- 6.1.8 Patients must abstain from alcohol during the blinded phase of the study.
- 6.1.9 Patient is available to attend all PK visits within the required visit window.
- 6.1.10 Patient and/or legal representative must be willing and able to give informed consent for participation in the study
- 6.1.11 Patient and/or legal representative must be willing and able (in the investigator's opinion) to comply with all study requirements.
- 6.1.12 Patient is willing for his or her name to be notified to the responsible authorities for participation in this study, as applicable.
- 6.1.13 Patient is willing to allow his or her primary care practitioner and consultant, if appropriate, to be notified of participation in the study.

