8. TREATMENT PROCEDURES

8.1 Investigational Medicinal Product Dosage, Administration and Schedule

The IMP will consist of three types of medication:

- GWP42003-P oral solution containing 100 mg/mL CBD.
- Placebo oral solution containing excipients.
- CLB (patient supplied).

The GWP42003-P/placebo will be presented as an oral solution containing either the active pharmaceutical ingredient and excipients (in the case of GWP42003-P) or only excipients (in the case of placebo). For details regarding GWP42003-P/placebo formulations, see [Section 5](#).

All patients will be weighed during the study visits and the daily volumes of GWP42003-P/placebo solution to be taken during the titration period, and for the remainder of the study, will be calculated and provided to the patient and/or caregiver. Further information on dispensing procedures will be provided in a separate Pharmacy Manual.

Each patient will take their first dose of GWP42003-P/placebo at Visit 2, Day 2 in the clinic. Patients not entering the OLE will take their final maintenance dose of GWP42003-P/placebo at Visit 4 (Day 33) in the clinic. Patients entering the OLE will take their final dose of IMP at Visit 11 (one year after the end of the blinded phase of the study) or sooner (if marketing authorization is granted within one year).

Patients will use their own supply of CLB throughout the study. Patients will continue on the dose that they were on at screening for the blinded phase of the study. CLB will only be an IMP for the blinded section of the study.

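### The no-effect rule for clobazam and N-CLB is applied to AUC(0-∞), a single-dose measure, although both PK days are at clobazam steady state; it exaggerates any change in the analyte's own elimination

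*Protocol*

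**What the plan says.** Inclusion criterion 6.1.6 states that "AED(s), including CLB, must be stable for four weeks prior to screening" and must stay so through the blinded phase. Section 8.1 adds: "Patients will continue on the dose that they were on at screening for the blinded phase of the study". Visit 2 follows screening by 7–14 days, and the second PK day is Day 33, after 21 days of maintenance.

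Section 13.6.1 says "The primary endpoints of the study are the PK parameters" Cmax, tmax, AUC(0-∞), AUC(0-t) and t½ for CLB and N-CLB, among other analytes. The synopsis and Section 4.1.1 carry the same list.

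Section 13.6.3 fixes the calculation. AUC(0-∞), the "Area under the concentration-time curve extrapolated to infinity", is AUC(0-t) + Clast/λz. For λz, "Linear regressions are repeated using the last three points with a quantifiable concentration, the last four points, the last five points etc", and the fit with the largest adjusted R² is kept. Sampling ends at 24 h, and the only times after 2 h are 4, 6, 12 and 24 h.

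The same section then uses "a standard 90% confidence interval (CI) approach for the between group ratios of geometric means of" Cmax, AUC(0-t) and AUC(0-∞). If the interval for a variable "falls within the interval [0.5, 2.0], a lack of meaningful effect will be declared". The synopsis repeats this rule. Neither place names an AUC over the dosing interval.

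**The concern.** After a single dose, AUC(0-∞) measures total exposure. At steady state the measure that reflects clearance is the AUC over one dosing interval. The tail Clast/λz then includes what is left of earlier doses, and a fall in clearance raises the result twice: once through the higher concentrations and again through the smaller λz.

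Two things are at stake. For AUC(0-∞), the limits 0.5 and 2.0 do not mean a halving or doubling of exposure. And one set of samples can give contradictory primary results on AUC(0-t) and AUC(0-∞) only because of the choice of metric.

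**Working it through.** **Inputs from the protocol.** CLB dose unchanged for at least 4 weeks before screening plus 7 days to Visit 2, so at least 35 days before the first profile; maintenance of 21 days before the second; sampling to 24 h; limits 0.5 and 2.0; 90% CI; 20 patients at 4:1, so 16 active and 4 placebo. There is no power or half-life figure in the protocol to reproduce.

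**Assumptions.** One compartment, once-daily dosing (τ = 24 h), half-life 12–100 h, both profiles at steady state, and an interaction that acts on clearance. At the long end the last is slightly generous: 21 days is 504 h, about 3.4 half-lives if 100 h lengthens to 150 h.

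**Step 1: formula.** At steady state AUC(0-τ) = F·Dose/CL, and the tail adds a fraction, so

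AUC(0-∞) = AUC(0-τ) / (1 − e^(−kτ)), with k = ln 2 / half-life.

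The extrapolated share is e^(−kτ): 25% at 12 h and 85% at 100 h. If clearance falls so that the true exposure ratio is r, k becomes k/r and the AUC(0-∞) ratio is

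r · (1 − e^(−kτ)) / (1 − e^(−kτ/r)),

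which approaches r² for long half-lives.

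**Step 2: numbers for r = 1.5.**
- Half-life 12 h: 1.5 × 0.750 / 0.603 = 1.87.
- Half-life 100 h: 1.5 × 0.1533 / 0.1050 = 2.19.

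| True ratio | AUC(0-∞) ratio, half-life 12 h to 100 h |
|---|---|
| 1.25 | 1.40 to 1.54 |
| 1.50 | 1.87 to 2.19 |
| 0.67 | 0.58 to 0.47 |

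Solving for the limits, AUC(0-∞) reaches 2.0 at a true ratio of 1.57 (12 h) to 1.43 (100 h), and 0.5 at 0.60 to about 0.69.

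**Step 3: effect on the decision.** Simulation with 16 paired patients (an illustrative size), true ratio 1.5, half-life 30 h, expected AUC(0-∞) ratio 2.07:

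| Within-patient CV | No effect declared on AUC(0-τ) | No effect declared on AUC(0-∞) |
|---|---|---|
| 20% | 0.99 | 0.02 |
| 30% | 0.84 | 0.03 |
| 40% | 0.64 | 0.03 |

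**Step 4: AUC(0-t).** With the protocol's own sampling times and linear trapezoid, once-daily AUC(0-t) over 24 h returns 1.99–2.00 when clearance is halved and 0.50–0.51 when it is doubled. It is already the dosing-interval AUC.

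**Step 5: N-CLB.** With an assumed CLB half-life of 30 h and N-CLB half-life of 20–80 h, the simulated peak-to-trough ratio is 1.01–1.05. Under the protocol's λz rule with 5–15% concentration noise (N-CLB half-life 24.5–80 h), 63–69% of profiles give no positive λz. A wider grid (CLB 12–42 h, N-CLB 6–80 h, noise 5–10%) gives 64–96%. Where N-CLB AUC(0-∞) is obtained at 24.5–80 h, noise alone gives it a log-scale SD of about 0.8–1.0, a factor of e^0.8 = 2.2 to e^1.0 = 2.7. For AUC(0-t) the log-scale SD is 0.02–0.07.

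**Step 6: twice-daily CLB.** The diary described in Section 4.1 records CLB morning and evening, and Sections 9.2.1.2.1 and 9.2.1.4.1 place the evening AED dose after the 12 h sample. For a patient who takes CLB twice daily, the 24 h point therefore follows a further dose, yet it enters every λz fit when it is quantifiable. In simulation (CLB half-life 18–42 h) λz is about 38% of its true value, and halved clearance appears as 3.79–3.89 against a true 2.0; once daily it appears as 3.24–3.63.

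**The case against.** The strongest reply is that little depends on AUC(0-∞). The rule is applied variable by variable, so a failure on AUC(0-∞) does not cancel a result on Cmax or AUC(0-t), and Section 13.1 calls the analysis descriptive. The bias pushes the ratio away from 1 and noise in λz widens the interval, so both work against declaring no effect. This stands and limits the severity. It does not remove the point, because Section 13.6.3 contains a declaration rule and AUC(0-∞) is one of the variables it covers.

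The second reply is that the exaggeration is not general. A pure change in bioavailability, or in N-CLB formation with N-CLB elimination unchanged, scales AUC(0-∞) and the dosing-interval AUC alike. The felbamate example in Section 3.3 is of the formation kind. This also stands. For CLB itself, however, Sections 3.3 and 3.4 make altered CYP metabolism the study hypothesis, so changed elimination is the expected case.

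Third, the half-lives and the flat N-CLB profile are assumed. That is so; the exaggeration holds at every half-life tried, but its size depends on them.

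A reader might also infer that the AUC(0-∞) analysis will rest on a chance remnant of 16 patients. The protocol does not support that. The PK set is all treated patients with some on-treatment data, placebo patients are not excluded from the model, a patient with one usable profile can stay in a mixed model, and the handling of inestimable λz may properly be left to the SAP.

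**Conclusion.** The point holds as a stated rule that uses the wrong metric. Where the analyte's own elimination changes, AUC(0-∞) at steady state exaggerates the exposure ratio: 1.5 becomes 1.87–2.19, and the nominal limits of 0.5 and 2.0 correspond to true ratios of about 0.60–0.69 and 1.43–1.57 (one compartment, once daily, assumed half-lives 12–100 h). If N-CLB is nearly flat over 24 h, its AUC(0-∞) is missing in about two thirds of profiles and very imprecise in the rest. Twice-daily CLB further corrupts λz.

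It is tempting to conclude that the trial could wrongly declare no interaction, or that its primary question is lost. Neither follows. The error is mainly a false or exaggerated interaction on one variable, in conflict with AUC(0-t). AUC(0-t) over 24 h is sound for once-daily CLB, so the primary objective can still be answered. This should be fixed, but it is not fatal.

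**What to change.** In Section 13.6.3 and in the synopsis under Statistical Considerations, apply the CLB and N-CLB no-effect rule to Cmax and to AUC over each patient's CLB dosing interval: 0–24 h if CLB is taken once daily, 0–12 h if twice daily. Remove AUC(0-∞) from the rule. Keep AUC(0-∞) and t½ for CLB and N-CLB as descriptive results, only where λz is estimable.

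Align the primary endpoint lists in the synopsis, Section 4.1.1 and Section 13.6.1 with this; otherwise the change creates a new contradiction.

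The cost is a protocol amendment. Because it alters listed primary endpoints, it may need ethics and authority approval under Section 16.1. The scheduled 12 h and 24 h samples suffice, so no new sampling is needed.

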13.6.4 Safety

13.6.4.1 Treatment Compliance and Extent of Treatment Exposure

Treatment compliance and exposure to treatment will be summarized for each phase of the study separately.

13.6.4.2 Adverse Events

AEs will be coded according to the Medical Dictionary for Regulatory Activities dictionary.

A treatment emergent AE is one that started, or worsened in severity or seriousness, following the first dose of IMP.

Descriptive presentations of treatment emergent AEs will be given by preferred term and system organ class for the safety analysis set. The number of patients reporting at least one AE will be provided. Summaries will be provided for each phase of the study separately.

The following summaries will be produced:

- All-causality AEs.
- Treatment related AEs.
- All-causality AEs by severity.
- All-causality serious AEs.
- Treatment related serious AEs.
- AEs reported as leading to permanent cessation of study treatment.
- Fatal AEs.

13.6.4.3 Clinical Laboratory Data

Clinical laboratory data at screening and at the end of the 31 day treatment phase and the change from baseline to end of treatment (OLE) will be summarized for the safety analysis set using appropriate summary statistics. Categorical shift tables will also be presented, showing the numbers of patients with values outside the normal range.

**13.6.4.4 Columbia-Suicide Severity Rating Scale, Vital Signs, 12-lead
Electrocardiogram, Physical Examination and Other Safety
Data**

The C-SSRS, vital signs, ECG and physical examination data will be summarized at screening, at the end of the 31 day treatment phase and during the OLE treatment period using appropriate summary statistics. Changes in the vital signs from baseline to end of each treatment phase will also be summarized.

13.6.4.5 Seizure Data

Seizure data collected during the 31 day treatment phase and during the OLE phase of the study will be summarized using appropriate summary statistics.

14. DATA SAFETY MONITORING COMMITTEE

GW does not plan to use an independent data safety monitoring committee as part of this study.

15. REGULATORY AND ETHICAL OBLIGATIONS

15.1 Declaration of Helsinki

The investigator will ensure that this study is conducted in full conformity with the^{31,35} and the clinical trial regulations adopting European Commission Directives into national legislation^{38,39,40}.

15.2 Informed Consent

Initial master ICFs will be provided to the investigator to prepare the informed consent documents to be used at his or her center. The GW Clinical Manager will communicate updates to the templates by letter. The written informed consent documents should be prepared in the language(s) of the potential patient population.

Before a patient's participation in the trial, the investigator is responsible for obtaining written informed consent from the patient or legal representative after adequate explanation of the aims, methods, anticipated benefits and potential hazards of the study and before any protocol specific screening procedures or any IMPs are administered. The patient, or their legal representative, should have ample time for review to consider the information provided before giving written consent; more specific definitions of ample time may be in force if required by IRB/ECs or local regulations.

The acquisition of informed consent should be documented in the patient's medical records and the ICF should be signed and personally dated by the patient or legal representative (as applicable) and by the person who conducted the informed consent discussion. GW also requires a physician to be present for consent and to sign the consent forms as well. The original signed ICFs should be retained and a copy provided to the patient or legal representative.

15.3 Institutional Review Board/Ethics Committee

A copy of the protocol, proposed ICFs, other patient information material, any proposed advertising material and any further documentation requested, must be submitted to the IRB/EC for written approval. GW must receive a copy of the written approval of the protocol and ICFs before enrollment of patients into the study and shipment of IMP.

The investigator must submit and, where necessary, obtain approval from the IRB/EC for all subsequent protocol amendments and changes to the informed consent documents. The investigator should notify the IRB/EC of deviations from the

protocol or SAEs occurring at the center and other AE reports received from GW, in accordance with local procedures.

The investigator will be responsible for obtaining on-going IRB/EC approval/renewal throughout the duration of the study. Copies of the investigator's reports and the IRB/EC continuance of approval must be sent to GW.

15.4 Pre-Study Documentation Requirements

The investigator is responsible for forwarding the following documents to GW for review before allowing any patients to consent for entry into the study:

- Signed and dated protocol signature page.
- Copy of approved ICFs and other patient information material.
- Copy of the IRB/EC approval of the protocol, ICFs and other patient information material.
- Up to date curricula vitae and medical licenses (as per local regulations) of the PI and all sub-investigators.
- The IRB/EC composition and/or written statement of the IRB/EC in compliance with the FDA regulations relating to GCP and clinical trials ^{32,33,34,41}, the EU Clinical Trials Directive ³⁵, or International Conference on Harmonization Tripartite Guideline for Good Clinical Practice (ICH GCP) ⁴² where the EU Directive does not apply.
- Signed laboratory normal ranges and documentation of laboratory certification (or equivalent) unless using central laboratory arranged by GW.
- Signed clinical trial agreement (including patient/investigator indemnity insurance and financial agreement).
- FDA 1572 form.
- Completed financial disclosure statements for the PI and all sub-investigators if relevant.

15.5 Participant Confidentiality

The investigator must ensure that the patient's anonymity is maintained. On the CRFs and within the databases used to collect the trial data or other documents submitted to GW, patients should be identified by their initials and race (if allowed per local regulations) and a patient study number only. Documents that are not for submission to GW, e.g., signed ICFs should be kept in strict confidence by the investigator.

In compliance with the FDA regulations relating to good clinical practice and clinical trials ^{32,33,34,41}, and the EU Clinical Trials Directive ³⁵/ICH GCP Guidelines ⁴², it is required that the investigator and institution permit authorized representatives of the company, the regulatory agencies and the IRB/EC direct access to review the patient's original medical records for verification of study related procedures and data. Direct

access includes examining, analyzing, verifying and reproducing any records and reports that are important to the evaluation of the study. The investigator is obligated to inform the patient that his/her study related records will be reviewed by the above named representatives without violating the confidentiality of the patient.

All information concerning the IMP and operations of GW such as patent applications, formulae, manufacturing processes, basic scientific data or formulation information supplied to the investigator by the company and not previously published is considered confidential by the company and shall remain the sole property of the company. The investigator will agree to use this information only in accomplishing the study and will not use it for any other purposes without the written consent of the company.

